### 3.0 STUDY ENDPOINTS

#### 3.1 Primary Endpoint

Determine overall response rate (ORR; ORR= Partial Response + Complete Response) at 2 months as measured by the [International Primary CNS Lymphoma Collaborative Group Response assessment criteria](#) [37] in subjects with relapsed/refractory primary and secondary CNS lymphoma receiving acalabrutinib.

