## 5.2 Toxicities and Dosing Delays/Dose Modifications

Any subject who receives at least one dose of acalabrutinib on this protocol will be evaluable for toxicity. Each subject will be assessed periodically for the development of any toxicity according to the [Time and Events table](#). Toxicity will be assessed according to the NCI Common Toxicity Criteria for Adverse Events (CTCAE), version 5.0.

If a subject experiences a toxicity or other intolerable AE suspected to be at least possibly related to acalabrutinib treatment during the course of therapy, then acalabrutinib should be withheld, as necessary, until the AE resolves or stabilizes to Grade  $\leq 1$  or baseline. Dose modifications for the following treatment-emergent toxicities are provided in **Table 2**. If/when treatment is resumed, the subject should proceed with the treatment schedule based on when the subject completed cycle 1 day 1; meaning that the schedule will not be paused when drug is held. If acalabrutinib is held for >14 consecutive days, then the subject should be permanently discontinued from study treatment and proceed to follow-up.

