## **5.5 Duration of Follow Up**

All subjects will be followed every 3 months ( $\pm 1$  month) for survival for 5 years or until death, whichever occurs first, starting from time the subject discontinues study treatment. To document survival, subjects will either be contacted directly, or their medical record will be checked. Subjects removed from treatment prior to progression (e.g. due to adverse event(s) or withdraw from treatment) will have imaging scans (MRI) annually for 2 years or until death, whichever occurs first, from the time they discontinue study treatment.

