9. MRI of brain should be obtained at screening within 28 days prior to start of study treatment and while on treatment at C3D1 ( $\pm 7$  days), C5D1 ( $\pm 7$  days), C7D1 ( $\pm 7$  days), C10D1 ( $\pm 7$  days), C13D1 ( $\pm 7$  days), C19D1 ( $\pm 7$  days), C25D1 ( $\pm 7$  days), and then annually ( $\pm 30$  days) for up to five years, or as needed, if there are any clinical signs/symptoms of progression. Scans will be continued until disease progression. If a subject comes off treatment for any reason other than disease progression (e.g. adverse events or withdraw from treatment), then the subject will have an MRI of the brain annually ( $\pm 30$  days) for up to 2 years or until disease progression.
10. Rubidium PET-CT performed at screening, C3D1 ( $\pm 7$  days), and C7D1 ( $\pm 7$  days), in the first 5 subjects at the University of North Carolina who consent to the procedure.
11. CT or PET-CT imaging will be performed at screening in order to confirm no evidence of systemic involvement of lymphoma. A prior scan showing no evidence of systemic involvement can be utilized, as long as it is performed within 28 days of starting study drug.
12. Ocular exams will be performed during screening only if the subject has ocular symptoms or recommended per standard of care. Subjects with active ocular lymphoma will have ophthalmologic evaluation (exam or imaging) to confirm CR.

13. Cerebrospinal fluid sample (3 – 4 mL) will be collected at 2 hours (+/- 1 hour) after oral administration of acalabrutinib at Cycle 1 Day 1 and Cycle 1 Day 8. Subjects who cannot have CSF samples drawn may remain in the study.
14. Acalabrutinib treatment will continue until the subject shows signs of disease progression, unacceptable toxicity, or withdraws from the study.
15. Toxicity assessment per NCI-CTCAE criteria, v.5.0.
16. Blood samples for pharmacokinetic analysis will be collected prior to acalabrutinib dosing and at 1, 2, and 4 hours after oral administration of acalabrutinib on Day 8 of Cycle 1. It is important to collect the time of last dose at each time point.
17. Testing of tumor sample for MYD88 and CXCR4 will be collected at baseline (Cycle 1 Day 1 prior to treatment initiation). Testing will only be carried out if there is sufficient tissue available. This may be from an archival sample or a fresh biopsy collection if collected per standard of care.

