**8.4 Assessment of Efficacy**

**8.4.1 The International Primary CNS Lymphoma Collaborative Group Response Assessment Criteria [37]**

Subjects who receive 1 cycle of acalabrutinib will be evaluable for efficacy. If a subject does not receive a full cycle of acalabrutinib they will not be evaluable and be replaced. The following criteria were developed on the basis of anatomic and radiographic definitions (**Table 3**). As additional radiographic, laboratory, or functional studies become more widely available and are demonstrated to have predictive value, they may be recommended as well.

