### 10.2 Sample Size, Accrual and Duration of Accrual

We plan to accrue up to 16 subjects to ensure planned (evaluable, in terms of status of overall response) sample size of 15. With 15 evaluable subjects, we reject the null hypothesis when we observe  $> 9$  (10 or more) responders. This design gives power 72% with one-sided type 1 error 0.15. We will replace non-evaluable (e.g., loss to follow-up) cases by new subjects to guarantee planned sample size.

Accrual for this trial is expected to take approximately 24-36 months.

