### 10.3 Data Analysis Plans

Analysis of efficacy will be conducted following pre-specified inference rule on rejecting the null hypothesis:  $H_0: \text{ORR} \leq 50\%$ . Specifically, we will reject the null hypothesis if and only if there are  $>9$  ORs in the 15 subjects. The main analysis is inferential because we frame it as a hypothesis-testing problem. We will also calculate 2-sided 95% clopper-Pearson confidence interval for ORR.

Secondary endpoints include PFS, CR, DoR, overall survival, and safety/toxicity. Analyses of secondary endpoints will be descriptive. Specifically, time-to-event outcomes like PFS, DoR, and OS will be analyzed using Kaplan-Meier method, and Kaplan-Meier survival curves will be provided. Categorical outcomes like CR, and safety/toxicity (different types of AEs) will be summarized using frequencies.

- For the primary outcome, ORR, there should be no missing data. We will replace non-evaluable cases with new subjects so that the total sample size of 15 evaluable subjects is guaranteed.
- There is only one test for the primary endpoint and hence there is no multiplicity issue.

Per exploratory endpoints:

[REDACTED]

[REDACTED]

[REDACTED]

[REDACTED]

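### A subject who completes cycle 1 and stops without progression on about Day 29 to 49 is evaluable for the primary endpoint but has no scheduled 2-month MRI

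*Combined protocol and SAP*

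**What the plan says.** - Section 3.1 sets the primary endpoint: "Determine overall response rate (ORR; ORR= Partial Response + Complete Response) at 2 months as measured by the" international PCNSL response criteria.
- Section 8.1, footnote 9, gives the scan schedule: "MRI of brain should be obtained at screening within 28 days prior to start of study treatment and while on treatment at C3D1", with a window of 7 days either side, and then at later cycles.
- The same footnote covers subjects who come off treatment for a reason other than progression ("e.g. adverse events or withdraw from treatment), then the subject will have an MRI of the brain annually"), within 30 days either way, for up to 2 years or until progression. Section 5.5 starts that clock at discontinuation: such subjects "will have imaging scans (MRI) annually for 2 years or until death, whichever occurs first, from the time they discontinue study treatment".
- In the Time and Events Table, the MRI row is empty in the End of Treatment column.
- Section 8.4.1 defines the efficacy set: "Subjects who receive 1 cycle of acalabrutinib will be evaluable for efficacy". It replaces only subjects who did not receive a full cycle, and it does not ask for a scan after baseline.
- Section 10.2 describes the 15 as evaluable with respect to overall response status and adds: "We will replace non-evaluable (e.g., loss to follow-up) cases by new subjects to guarantee planned sample size".
- Section 10.3 states: "For the primary outcome, ORR, there should be no missing data".
- Section 5.2 provides one route off treatment: "If acalabrutinib is held for >14 consecutive days, then the subject should be permanently discontinued from study treatment". The visit schedule is not paused during a hold.

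**The concern.** Evaluability is fixed at about Day 28, but the endpoint is read at about Day 57, and the scan that supplies it depends on still taking the drug. A subject who stops in between for toxicity or by choice is counted in the 15, yet no scheduled procedure shows whether the subject responded. The gap is tied to tolerability, so these subjects are not a random subset.

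The plan then points three ways: keep the subject (8.4.1), possibly replace the subject (10.2), or assume the case does not arise (10.3). It never says how to classify an evaluable subject without a 2-month scan. With 15 subjects and a fixed cutoff of 10 responders, one classification can decide the result. Suppose 9 of 14 scanned subjects have responded and one is unscanned. Scored as a non-responder, the result is 9 of 15 and the null hypothesis stands. Replaced by a subject who responds, it is 10 of 15 and the null is rejected. That choice should not be left until the data are known.

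**Working it through.** **The plan's own figures.** Inputs from Sections 10.1 and 10.2: 15 evaluable subjects, rejection at 10 or more responders, ORR 50% against 70%.
- Type I error = P(Bin(15, 0.5) ≥ 10) = 0.151; the plan states 0.15.
- Power = P(Bin(15, 0.7) ≥ 10) = 0.722; the plan states 72%.

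Both are reproduced to the precision printed.

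**Timing.** Cycles are 28 days.
- C3D1 = 1 + 2 × 28 = Day 57; window 57 ± 7 = Day 50 to 64.
- Cycle 1 ends on Day 28. A stop on Day 29 to 49 comes after the one-cycle rule is met and before the window opens.
- First planned off-treatment MRI = stop day + 365 ± 30, that is 335 to 395 days after stopping. A stop on Day 29 gives study Day 364 to 424; a stop on Day 49 gives Day 384 to 444.
- End of Treatment visit (footnote 1) = stop day + 30 ± 7. A stop on Day 29 gives Day 52 to 66, which overlaps the MRI window, but no MRI is listed. The overlap lasts while stop day + 23 ≤ 64, so for stops up to Day 41.

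**Route through the hold rule.** A hold that starts on day h passes 14 consecutive days on day h + 14. For h = 29 that is Day 43; for h = 35, Day 49. Holds starting on Day 29 to 35 therefore lead to discontinuation inside the gap. Outright stops on Day 29 to 49 fall in it as well.

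**Effect if unscanned subjects are scored as non-responders.** With m such subjects among the 15, the 10 responders must come from the other 15 − m. The documents give no value for m, so it is an assumption. Type I error is P(Bin(15 − m, 0.5) ≥ 10) and power is P(Bin(15 − m, 0.7) ≥ 10).

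| m | Type I error | Power |
|---|---|---|
| 0 | 0.151 | 0.722 |
| 1 | 0.090 | 0.584 |
| 2 | 0.046 | 0.421 |

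**Effect if they are replaced.** Fifteen subjects then have a known status and nominal power stays at 0.722, but the ORR describes only subjects who were scanned. For example, 10 responders among 15 scanned is 66.7%; counting one replaced subject as a non-responder makes it 10 of 16, or 62.5%. Accrual of up to 16 leaves room for only one replacement.

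**The case against.** The strongest reply is that the gap is narrow and other provisions may cover it. Part of that stands.

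- **Width.** A reader might infer that any stop between Day 29 and Day 56 loses the scan. The documents do not support that: the window opens on Day 50, so a subject who stops on Day 50 to 56 may already have been scanned. Nor does every hold beginning between Day 15 and Day 42 produce such a subject. A hold from Day 15 to 28 misses cycle 1 doses and may fail the full-cycle rule. A hold from Day 36 to 42 reaches the 14-day limit only once the window is open.
- **Other scans.** Footnote 9 allows MRI as needed for signs or symptoms of progression, so it would be too strong to say that outcome is never observed. But those scans are triggered by suspected progression and tend to find failures, not responses. Section 5.6 asks for a complete final evaluation at withdrawal from the study; it does not name MRI and does not apply to stopping treatment alone. Under Section 5.7 a new anticancer therapy takes the subject off study, so even the yearly scan may not happen.
- **Power.** The losses in the table are not what the plan prescribes. They apply only if unscanned subjects are scored as non-responders, which the plan does not say.
- **Frequency.** A reader might attach a rate of cycle 2 stopping. The documents give none. The pooled figure in Section 1.4.2 (26.3% with Grade 3 or higher treatment-related events, median exposure 28.5 months, other hematologic malignancies) cannot be turned into one.
- **Pilot status.** This does not remove the point. Section 10.3 calls the main analysis inferential and sets an exact rejection rule, so each subject's status must be defined.

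**Conclusion.** The concern holds for subjects who complete cycle 1 and stop acalabrutinib without progression on about Day 29 to 49. They are evaluable under 8.4.1, have no scheduled MRI in the Day 50 to 64 window, and are next due a scan about a year after stopping. Sections 8.4.1, 10.2 and 10.3 do not agree on what to do with them.

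The timing follows from the documents alone. The number affected is unknown. If such subjects are scored as non-responders, one costs about 14 percentage points of power at a 70% ORR (0.722 to 0.584) and two cost about 30 (0.722 to 0.421), with type I error falling as well. If they are replaced, nominal power is kept but early toxicity stops leave the ORR. These figures assume that the remaining subjects respond independently at the stated rates. The documents do not support a wider gap, a particular stopping rate, or a power loss as the plan's own consequence.

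**What to change.** 1. In footnote 9 and Section 5.5, add: *The 2-month response MRI (Day 57 ± 7) is done in every subject who completed cycle 1 and is alive without documented progression, whether or not still on treatment, and before any new anticancer therapy where possible.* For stops up to Day 41 it can share the End of Treatment visit.
2. In Sections 8.4.1, 10.2 and 10.3, state in the same terms: *A subject with one completed cycle and no 2-month response assessment, including one lost to follow-up after cycle 1, stays among the 15 as a non-responder and is not replaced.* Section 10.2 must change too, because its loss-to-follow-up example would otherwise still replace such a subject. The no-missing-data statement in 10.3 should be reworded to match.

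If every such scan is obtained, all 15 have a response status and the design keeps type I error 0.151 and power 0.722. The cost is an off-treatment MRI for a few subjects and, wherever the scan is still missing, a lower ORR and the power loss shown above.

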## 8.2 Handling of Biospecimens Collected for Correlative Research

Biospecimens collected for this study will be stored in the Lineberger Comprehensive Cancer Center (LCCC) Tissue Procurement Facility (TPF), or if needed, in a secure off-site storage facility. All biospecimen samples will be obtained in accordance with procedures outlined in the LCCC1841 Study Laboratory Manual and stored in containers with controlled access. Each sample will be assigned a unique code number and no identifiable personal health information (PHI) will be on the specimen label. Information about the subject's disease will be linked to the specimens stored in the repository database. TPF-associated research staff, LCCC Bioinformatics staff who support the TPF database and the LCCC Data Warehouse, and researchers with IRB-approval for access to PHI for each subject in this study will be able to link specimens to relevant medical information. Some results from laboratory analyses that occurred during the subject's participation in the clinical study may also be included. This information may be important for understanding how the subject's cancer developed and responded to treatment.

### *Storage Time:*

- The biospecimen will be used first and foremost for research purposes outlined within the confines of this protocol. Samples will be discarded/destroyed after relevant data are collected for this study, unless consent was obtained from the subject to use tissue for other research purposes (e.g., TPF consent form was signed by the subject). Specimens will be stored for 10 years.
  - The investigator must agree to abide by policies and procedures of the TPF facility and sign a letter of research agreement for ethical and appropriate conduct of their research that utilizes specimens obtained from the TPF

facility (e.g., Use of leftover specimens will require a protocol outlining the research plan for biospecimen use).

*Compliance Statement*

Biospecimen collection for this study will be conducted in full accordance to all applicable University of North Carolina (UNC) Research Policies and Procedures and all applicable Federal and state laws and regulations including 45 CFR 46, and the Health Insurance Portability and Accountability Act (HIPAA) Privacy Rule. Any episode of noncompliance will be documented.

The investigators will perform the study in accordance with this protocol, will obtain consent and assent (unless a waiver is granted), and will report unexpected problems in accordance with The UNC IRB Policies and Procedures and all federal requirements. Collection, recording, and reporting of data will be accurate and will ensure the privacy, health, and welfare of research subjects during and after the study.

**8.3 Assessment of Safety**

Any subject who receives at least one dose of acalabrutinib on this protocol will be evaluable for toxicity. Each subject will be assessed periodically for the development of any toxicity according to the [Time and Events table](#). Toxicity will be assessed according to the NCI CTCAE v5.0.

**8.4 Assessment of Efficacy**

**8.4.1 The International Primary CNS Lymphoma Collaborative Group Response Assessment Criteria [37]**

Subjects who receive 1 cycle of acalabrutinib will be evaluable for efficacy. If a subject does not receive a full cycle of acalabrutinib they will not be evaluable and be replaced. The following criteria were developed on the basis of anatomic and radiographic definitions (**Table 3**). As additional radiographic, laboratory, or functional studies become more widely available and are demonstrated to have predictive value, they may be recommended as well.

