## 5.0 TREATMENT PLAN

### 5.1 Schema

Figure 1 Study Schema

LCCC 1841 is a multicenter open-label, single-arm, pilot study designed to investigate the antitumor effects of acalabrutinib in subjects with relapsed primary central nervous system (CNS) lymphoma, and relapsed secondary CNS lymphoma with no evidence of current systemic disease. Rb PET/CT will be performed at screening, at Cycle 3 Day 1 and at Cycle 7 Day 1 in the first 5 subjects at the University of North Carolina with parenchymal brain disease who consent to this testing. Subjects will continue on treatment until disease progression or discontinuation of treatment due to an adverse event. During the study, 15 evaluable subjects (per [section 8.4](#)) will be enrolled and treated. Up to 16 subjects (15 evaluable subjects) will receive acalabrutinib at the dose of 100 mg every 12 hours (**Table 1**).

Table 1 Treatment dosage and administration

REGIMEN DESCRIPTION					
Agent	Precautions	Dose	Route	Schedule	Cycle Length
Acalabrutinib	Take acalabrutinib with or without food	100mg	oral	Every 12 hours	4 weeks (28 days)

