## 10.0 STATISTICAL CONSIDERATIONS

### 10.1 Study Design

As the first study of acalabrutinib in relapsed/refractory CNS lymphoma, LCCC1841 study is designed as an open label, single arm pilot study to provide preliminary data about its efficacy before proceeding to a larger two arm study. Furthermore, since this is a rare lymphoma, it would take an unreasonable amount of time and multiple centers would be needed to enroll an adequate number of subjects for a randomized phase 3 study.

The null hypothesis is:  $H_0: \text{ORR} \leq 50\%$  vs  $H_1: \text{ORR} \geq 70\%$  (i.e., 20% improvement). We plan to obtain 15 evaluable patients in this pilot study.

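### Treated subjects who fail during cycle 1 leave the ORR denominator and are replaced, so ORR is biased upward, the 0.15 type I error holds only for the evaluable subset, and the cap of 16 cannot guarantee 15 evaluable

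*Combined protocol and SAP*

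**What the plan says.** All references are to the combined protocol and SAP.

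- **Evaluability.** Section 8.4.1: "If a subject does not receive a full cycle of acalabrutinib they will not be evaluable and be replaced". Sections 1.1 and 5.1 refer to Section 8.4 for the meaning of evaluable.
- **Replacement.** Section 10.2: "We will replace non-evaluable (e.g., loss to follow-up) cases by new subjects to guarantee planned sample size". Loss to follow-up is given there only as an example. Section 10.3 repeats the replacement and concludes: "For the primary outcome, ORR, there should be no missing data".
- **Cap.** Section 5.1: "Up to 16 subjects (15 evaluable subjects) will receive acalabrutinib". Section 10.2 says the same: "We plan to accrue up to 16 subjects to ensure planned (evaluable, in terms of status of overall response) sample size of 15".
- **Decision rule.** Section 10.3: "we will reject the null hypothesis if and only if there are $>9$ ORs in the 15 subjects". Section 10.2 states power 72% and one-sided type I error 0.15, for a null ORR of 50% and an alternative of 70% (Section 10.1).
- **Target population.** The primary objective (Section 2.1) and primary endpoint (Section 3.1) are worded for people given acalabrutinib, with response read at 2 months. Toxicity is assessed in everyone with at least one dose (Sections 5.2 and 8.3).

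The visible text contains no ORR analysis in all treated subjects and no rule that counts early failures as non-responders.

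**The concern.** Treatment ends at progression or an unacceptable adverse event (Sections 5.1 and 5.4), and a hold of more than 14 consecutive days means permanent discontinuation (Section 5.2). A subject who progresses, dies or stops for toxicity within the first 28 days therefore does not complete the cycle. Under Section 8.4.1 that subject is not a non-responder but leaves the denominator, and a new subject takes the place. ORR is then estimated among people who got through a month of drug, which is not the population in the objective. Removing non-responders can only push it up.

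Two related problems follow from the same text. With at most 16 accrued there is room for one replacement, so 15 evaluable subjects cannot be guaranteed, and the plan gives no rule for fewer than 15. Also, Section 8.4.1 defines evaluability by cycles received and Section 10.2 by known response status. A subject who finishes cycle 1 but has no Cycle 3 Day 1 MRI is not clearly placed, and in an open-label trial that could be settled after outcomes are known.

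At stake is the go/no-go decision. Section 10.3 calls the primary analysis inferential, and Section 1.1 ties further investigation to the ORR.

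**Working it through.** **Inputs from the documents.** Null ORR 0.50 and alternative 0.70 (Section 10.1); 15 evaluable, at most 16 accrued, success at 10 or more responders (Sections 10.2 and 10.3).

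**Assumptions.** Let q be the share of treated subjects who fail before completing cycle 1, all of them non-responders. The documents give no value, so q runs over 5, 10, 15 and 20%. The true ORR in all treated subjects is held at the null, 0.50.

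**Step 1: the plan's own figures.** P(X ≥ 10 | n = 15, p = 0.50) = (3003 + 1365 + 455 + 105 + 15 + 1)/32768 = 4944/32768 = 0.1509. P(X ≥ 10 | 15, 0.70) = 0.7216. Both agree with the stated 0.15 and 72%.

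**Step 2: ORR among evaluable subjects.** Dropping the early failures leaves 0.50/(1 − q). For q = 10%: 0.50/0.90 = 0.556.

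**Step 3: probability of 10 or more responders with the cap.** A 16th subject enters only if one of the first 15 was an early failure. Success needs either 10 or more responders in the first 15, or exactly 9 there, at least one early failure among the other 6, and a response in the 16th. Given non-response, the chance of an early failure is q/0.50 = 2q. So

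P = 0.1509 + (5005/32768) × [1 − (1 − 2q)^6] × 0.50.

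For q = 5%: 0.1509 + 0.1527 × 0.4686 × 0.50 = 0.187. The ceiling is P(X ≥ 10 | 16, 0.50) = 14893/65536 = 0.227.

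**Step 4: probability that 15 evaluable subjects are not reached.** This requires at least two early failures in 16: 1 − (1 − q)^16 − 16q(1 − q)^15. For q = 10%: 1 − 0.1853 − 0.3294 = 0.485.

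**Step 5: two other readings.** If success is allowed only with exactly 15 evaluable, the probability is (1 − q)^15 × (1 + 15q) × T, where T = P(X ≥ 10 | 15, 0.50/(1 − q)). T alone applies if replacement continues without limit, or conditional on having reached 15.

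| q | Evaluable ORR | ≥10 responders, cap 16 | Fewer than 15 evaluable | ≥10 and exactly 15 evaluable, cap 16 | T: unlimited replacement, or given 15 reached |
|---|---|---|---|---|---|
| 5% | 0.526 | 0.187 | 0.189 | 0.166 | 0.204 |
| 10% | 0.556 | 0.207 | 0.485 | 0.142 | 0.275 |
| 15% | 0.588 | 0.218 | 0.716 | 0.104 | 0.367 |
| 20% | 0.625 | 0.224 | 0.859 | 0.068 | 0.483 |

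**Step 6: one concrete trial.** Sixteen treated, one early failure, 10 responders. The plan reports 10/15 = 66.7% (95% Clopper-Pearson interval 38.4 to 88.2) and declares success. In all treated it is 10/16 = 62.5% (35.4 to 84.8), and a cut-off of 10 in 16 has type I error 0.227.

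**Step 7: power if early failures count as non-responders.** With 15 dosed and ORR 0.70 in all dosed, power stays 0.7216. If 70% describes only subjects who complete cycle 1, the all-dosed rate is 0.70(1 − q). At q = 5% this is 0.665 and power is 0.613; at q = 10% it is 0.63 and power is 0.499.

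**The case against.** **The 0.15 is correct for the population the design names.** Sections 10.1 and 10.2 specify 15 evaluable subjects, and for them 0.1509 is exact. This stands. A reader might infer a calculation error; there is none. The fault is a mismatch between the tested subset and the population in Sections 2.1 and 3.1.

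**The cap contains the inflation.** This also stands. Because Sections 10.2 and 10.3 promise 15, a reader might infer that the false-positive probability can climb towards 0.48. That needs replacement without limit, or conditioning on having reached 15, and the cap of 16 rules out the first.

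**Read strictly, the rule may not inflate at all.** If a decision requires exactly 15 evaluable, rejection under the null is 0.166 at 5% early failure and below 0.15 from 10%. True, but only because the trial then often ends with no decision.

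**Early failures may be rare.** Eligibility requires ECOG 2 or better and excludes life-threatening illness judged to compromise safety. The first scheduled on-treatment MRI is at Cycle 3 Day 1, so progression in cycle 1 would have to surface clinically, and progression after cycle 1 stays in the denominator. All this is fair: with no cycle-1 failure there is no bias. Nor do the documents show that subjects lost in cycle 1 would mostly be treatment failures; that is an assumption of the calculation.

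**Two further inferences are not supported.** One is that a brief dose hold makes a subject non-evaluable. Full cycle is undefined, but Section 5.2 keeps the schedule running during a hold, so exclusion is only one reading. The other is that PFS and OS carry guaranteed survival time from the one-cycle requirement. Section 10.3 names no set for them, but Table 3 lists both for all patients from trial entry.

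**It is a pilot with a loose error rate.** That lowers the stakes but does not excuse the denominator, since a formal test is made and used.

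**Conclusion.** The concern holds in this form. As written, the plan removes and replaces treated subjects who fail in cycle 1, which biases ORR upward for the population in the objective whenever that happens. The type I error of 0.15 applies to the evaluable subset only. Against an all-treated ORR of 50%, the capped design gives 10 or more responders with probability between 0.187 and 0.224 over the assumed 5 to 20% range: a moderate inflation with a firm ceiling.

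The second defect does not depend on how the null is framed. The cap and the promise of 15 evaluable cannot both hold. At 10% early failure the chance of having no defined decision is close to one half.

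These sizes rest on the assumed q, on every early failure being a non-responder, and on independent subjects.

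**What to change.** In Sections 8.4.1, 10.2 and 10.3:

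- Define the primary ORR set as the first 15 subjects who receive at least one dose.
- Count as a non-responder anyone without a documented response at the 2-month (Cycle 3 Day 1) assessment, including early progression, death, stopping for toxicity, withdrawal and a missing scan. Leave the definition of response in Section 3.1 as it is.
- Replace only subjects who are never dosed, and align the accrual wording in Sections 1.1 and 5.1.
- Keep the rule of 10 or more in 15, which then has type I error 0.1509 for the population in the objective.
- Report ORR in the one-cycle evaluable set as a sensitivity analysis.

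The denominator should stay at 15. If all 16 dosed were used instead, the cut-off would have to be reset: 10 or more gives type I error 0.227 and power 0.825; 11 or more gives 0.105 and 0.660.

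**Cost.** A wording change and no extra subjects. The reported ORR may be lower. The plan should also say which population the 70% target describes: if only cycle-1 completers, it should disclose the power loss in step 7, from 0.72 to about 0.61 at 5% and 0.50 at 10% early failure.
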